3.3.3 Exclusion criteria

Subjects will not be allowed to participate if any of the following general criteria apply:

1. Any finding in the medical examination (including BP, PR or ECG) is deviating from normal and judged as clinically relevant by the investigator

Proprietary confidential information © 2017 Boehringer Ingelheim International GmbH or one or more of its affiliated companies

2. Repeated measurement of systolic blood pressure outside the range of 90 to 140 mmHg, diastolic blood pressure outside the range of 50 to 90 mmHg, or pulse rate outside the range of 45 to 90 bpm
3. Any laboratory value outside the reference range that the investigator considers to be of clinical relevance
4. Any evidence of a concomitant disease judged as clinically relevant by the investigator
5. Gastrointestinal, hepatic, renal, respiratory, cardiovascular, metabolic, immunological or hormonal disorders
6. Diseases of the central nervous system (including but not limited to any kind of seizures or stroke), and other relevant neurological or psychiatric disorders
7. History of relevant orthostatic hypotension, fainting spells, or blackouts
8. Chronic or relevant acute infections including active tuberculosis, HIV or viral hepatitis; QuantiFERON TB test will be performed at screening.
9. History of relevant allergy or hypersensitivity (including allergy to the trial medication or its excipients)
10. Use of drugs within 30 days prior to administration of trial medication if that might reasonably influence the results of the trial (incl. QT/QTc interval prolongation)
11. Participation in another trial where an investigational drug has been administered within 5 half-lives prior to planned administration of trial medication, or current participation in another trial involving administration of investigational drug.

13. Administered live vaccine within 6 weeks prior to randomisation or Have plans for administration of live vaccines during the study period.
14. Smoker (more than 10 cigarettes or 3 cigars or 3 pipes per day)
15. Inability to refrain from smoking on specified trial days
16. Alcohol abuse (consumption of more than 30 g per day)
17. Drug abuse or positive drug screening
18. Blood donation of more than [REDACTED] within 30 days prior to administration of trial medication or intended donation during the trial
19. Intention to perform excessive physical activities within one week prior to administration of trial medication or during the trial
20. Inability to comply with dietary regimen of trial site
21. A marked baseline prolongation of QT/QTc interval (such as QTc intervals that are repeatedly greater than 450 ms in males) or any other relevant ECG finding at screening
22. A history of additional risk factors for Torsades de Pointes (such as heart failure, hypokalemia, or family history of Long QT Syndrome)
23. Subject is assessed as unsuitable for inclusion by the investigator, for instance, because considered not able to understand and comply with study requirements, or has a condition that would not allow safe participation in the study

For study restrictions, refer to [Section 4.2.2](#).

3.3.4 Removal of subjects from therapy or assessments

3.3.4.1 Removal of individual subjects

An individual subject is to be removed from the trial if:

1. The subject withdraws consent, without the need to justify the decision
2. The subject needs to take concomitant drugs that interfere with the investigational product or other trial medication
3. The subject is no longer able to participate for other medical reasons (such as surgery, adverse events, or diseases)
4. An AE or clinically significant laboratory change or abnormality occurred that the investigator judges to warrant discontinuation of treatment. This may include cases of sustained symptomatic hypotension (BP <90/50 mmHg) or hypertension (BP >180/100 mmHg) or of clinically relevant changes in ECG requiring intervention as well as unexplained liver enzyme elevations at any time during the trial.
5. The subject shows an elevation of AST and/or ALT ≥ 3 -fold ULN combined with an elevation of total bilirubin ≥ 2 -fold ULN (measured in the same blood sample) and/or needs to be followed up according to [Section 10.1](#) of this clinical trial protocol and the 'DILI checklist' provided in the ISF.

In addition to these criteria, the physician may discontinue subjects at any time based on his or her clinical judgment.

Infusion reactions should also lead to the removal of an individual subject. However, in mild transient cases of infusion reactions (with clinical symptoms such as dizziness, headache, nausea) requiring no treatment the clinical investigator may continue [[P16-06636](#)]. However, the overall infusion time must not exceed 90 minutes.

A subject can also be removed from the trial if eligibility criteria are being violated or if the subject fails to comply with the protocol (for instance, by non-adherence to dietary rules, or non-attendance at study assessments).

If a subject is removed from or withdraws from the trial prior to first administration of trial medication, the data of this subject will not be entered in the case report form (CRF) or trial database and will not be reported in the clinical trial report (CTR). The only exception to this rule is when the subject had an AESI and/or SAE that the investigator considers related to the screening procedure. If a subject is removed from or withdraws from the trial after administration of trial medication, this will be documented and the reason for discontinuation must be recorded in the CRF. In this case, the data will be included in the CRF/trial database and will be reported in the CTR. At the time of discontinuation a complete end of trial examination will be performed if possible and the information will be recorded in the CRFs. If the discontinuation occurs before the end of the REP (see [Section 5.2.2.2](#)), the discontinued subject should if possible be questioned for AEs and concomitant therapies at or after the end of the REP in order to ascertain collection of AEs and concomitant therapies throughout the REP, if not contrary to any consent withdrawal of the subject. These discontinuations will be discussed in the CTR.

Proprietary confidential information © 2017 Boehringer Ingelheim International GmbH or one or more of its affiliated companies

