11. Safety laboratory is to be taken within three days prior to study drug administration and can be omitted, if the screening examination is performed between Day -5 to Day -3.
12. First measure after completion of infusion collection of PK sample

Proprietary confidential information © 2017 Boehringer Ingelheim International GmbH or one or more of its affiliated companies

FLOW CHART

(sc) Single dose group

Visit	Day	Time relative to first drug administration (planned time [h:min])	Approx. time (actual time) [h:min]	Event and comment	PK _{blood} ⁴	Laboratory/ Urinalysis ³	Body Temperature	12-lead ECG	ECG monitoring	Vital signs (BP, PR)	Query on adverse events, concomitant therapies ⁹
1	-28 to -3			screening ¹		X		X		X	
	-3 to -1	-72:00	8:00	ambulatory visit		X ¹¹					
	-1	-12:00	20:00	admission to trial site							X
	1	-2:00	6:00	randomisation and pre-dose ²	X	X	X	X		X	X ⁵
		0:00	8:00	drug administration					▲		
		0:30	8:30		X		X			X	X ⁵
		1:00	9:00							X	
		1:30	9:30		X					X	
		2:00	10:00		X		X	X	▼	X	
		3:00	11:00		X					X	
		4:00	12:00	Lunch ⁶	X	X				X	X ⁵
		6:00	14:00				X	X		X	
		8:00	16:00		X					X	
	2	10:00	18:00	Dinner ⁶							
		12:00	20:00		X		X	X		X	X ⁵
		24:00	8:00	Breakfast ⁶	X	X	X	X		X	X ⁵
		28:00	12:00	Lunch ⁶							
3	2	32:00	16:00				X			X	
		34:00	18:00	Dinner ⁶							X ⁵
		48:00	8:00	Discharge from trial site (confirmation of fitness) ⁷	X			X		X	X ⁵
		72:00	8:00	ambulatory visit	X	X					X ⁵
		96:00	8:00	ambulatory visit	X						X ⁵
4		168:00	8:00	ambulatory visit	X	X		X		X	X ⁵
5		336:00	8:00	ambulatory visit	X						X ⁵

Proprietary confidential information © 2017 Boehringer Ingelheim International GmbH or one or more of its affiliated companies

FLOW CHART (cont.)

Visit	Day	Time relative to first drug administration (planned time [h:min])	Approx. time (actual time) [h:min]	Event and comment	PK _{blood} ⁴	Laboratory/ Urinalysis ³	Body Temperature	12-lead ECG	ECG monitoring	vital signs (BP, PR)	Query on adverse events, concomitant therapies ⁹
2	22	504:00	8:00	ambulatory visit	X	X		X		X	X ⁵
	29	672:00	8:00	ambulatory visit	X	X		X		X	X ⁵
	36	840:00	8:00	ambulatory visit	X						X ⁵
	43	1008:00	8:00	ambulatory visit	X						X ⁵
	57	1344:00	8:00	ambulatory visit	X						X ⁵
	71	1680:00	8:00	ambulatory visit	X						X
	92±2	2184:00	8:00	ambulatory visit	X						X
	120±3	2856:00	8:00	ambulatory visit	X						X
3	148±3	3528:00	8:00	EOT ¹⁰	X ¹²		X		X	X	X ⁵

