4.1.4 Drug assignment and administration of doses for each subject

The treatments to be evaluated are outlined in Table 4.1.4: 1 below. Each subject will receive one single dose of trial medication. The dose volume for placebo corresponds to the dose volume of the respective dose level. For further details concerning timing see [Flow Chart](#). Detailed instructions for the preparation are provided in ISF.

Table 4.1.4: 1 Final dose of BI 655130 in solution containing active drug

Dose group	Final dose of BI 655130 [■]
1	[■] (intravenous infusion)
2	[■] (intravenous infusion)
3	[■] (intravenous infusion)
4	[■] subcutaneous injection)

For intravenous administration

The detailed instructions for the dilution of the trial product, the preparation of the infusion solution and the volume to be administered is provided in ISF. In all subjects the infusion solution will be intravenously administered over 90 minutes approximately between 8:00 and 10:00 of the respective study day. Start and end time of the infusion will be recorded.

In case of safety concerns, e.g. due to infusion reactions, the investigator or his/her designee should stop of the infusion. Further based on medical judgment he/she will provide medications such as steroids, etc. as needed.

For administration of the infusion, an intravenous indwelling catheter is placed into an arm vein of the subject and will be kept patent with a saline infusion. A second indwelling catheter used for collection of blood samples will be placed on the contralateral arm.

The administration of the trial medication on all study days will be done under supervision of the investigating physician or a designee. The so-called four-eye principle (two-person rule) should be applied for administration of trial medication and – if applicable – its preparation (e.g. reconstitution), if correct dosage cannot be ensured otherwise. For the purpose of drug accountability, the infusion set will be weighed before and after drug administration.

Water is allowed except for 1 hour before start of infusion and 1.5 h after end of infusion.

For subcutaneous administration

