6. INVESTIGATIONAL PLAN

6.1 VISIT SCHEDULE

Exact times of measurements outside the permitted time windows will be documented. The acceptable time windows for screening, observation visit, and end of trial examination are given in the Flow Chart.

Study measurements and assessments scheduled to occur 'before' trial medication administration on Day 1 are to be performed and completed within a 2 h-period prior to the trial drug administration (including blank values for PK).

The acceptable deviation from the scheduled time for vital signs and ECG will be:

- ± 15 min up to including 12 h
- ± 30 min from 12h up to including 48 h
- ± 60 min from 48 h up to Day 8
- ± 24 h from Day 15 up to Day 71
- ± 48 h on Day 92
- ± 72 h from Day 120 up to the last measurements

The tolerance for pharmacokinetic/ADA/laboratory parameters will be:

- ± 1 min up to including 1 h
- ± 5 min up to including 12 h
- ± 15 min up to including 48 h
- ± 60 min from 48 h up to Day 8
- ± 24 h from Day 15 up to Day 71
- ± 48 h on Day 92
- ± 72 h from Day 120 up to the last measurements

If scheduled in the [Flow Chart](#) at the same time as a meal, blood sampling, vital signs and 12-lead ECG recordings have to be done first. Furthermore, if several measurements including venipuncture are scheduled for the same time, venipuncture should be the last of the measurements due to its inconvenience to the subject and possible influence on physiological parameters.

For planned individual plasma concentration sampling times refer to the Flow Chart. While these nominal times should be adhered to as closely as possible, the actual sampling times will be recorded and used for determination of pharmacokinetic parameter.

If a subject misses an appointment, it will be rescheduled if possible. The relevance of measurements outside the permitted time windows will be assessed no later than at the Report Planning Meeting.

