7.3.2 Secondary analyses

The secondary parameters (refer to [Section 5.5.1](#)) will be calculated according to the BI Standard Operating Procedure (SOP) ‘Standards and processes for analyses performed within Clinical Pharmacokinetics/Pharmacodynamics’ ([001-MCS-36-472](#)). Analyses will be performed for parent drug.

Plasma concentration data and parameters of a subject will be included in the statistical PK

Proprietary confidential information © 2017 Boehringer Ingelheim International GmbH or one or more of its affiliated companies

analysis if they are not flagged for exclusion due to a protocol violation relevant to the evaluation of PK (to be decided no later than in the Report Planning Meeting) or due to PK non-evaluability (as revealed during data analysis, based on the criteria specified below). Exclusion of a subject's data will be documented in the CTR.

Relevant protocol violation may be:

- Incorrect trial medication taken, i.e. the subject received trial medication the subject was not assigned to
- Incorrect dose of trial medication taken
- Use of restricted medications.

Plasma concentrations and/or parameters of a subject will be considered as non-evaluable, if for example

- Missing samples/concentration data at important phases of PK disposition curve.

The PK parameter analysis set (PKS) includes all subjects in the treated set who provide at least one PK parameter that was not excluded according to the description above.

Assessment of dose proportionality

Dose proportionality will be assessed for $AUC_{0-\infty}$ and C_{max} in intravenous doses.

The basic model for the investigation of dose proportionality will be a power model that describes the functional relationship between the dose and PK endpoints.

$$\exp(Y_{ij}) = \alpha' * \exp(X_i)^\beta * \varepsilon'_{ij}$$

The model consists of a regression model applied to log-transformed data. The corresponding ANCOVA model includes the logarithm of the dose as a covariate.

Together with $\alpha' = \exp(\alpha)$ and $\varepsilon'_{ij} = \exp(\varepsilon_{ij})$, taking natural logarithms converts this model to a linear form as follows:

$$Y_{ij} = \alpha + \beta * X_i + \varepsilon_{ij}$$

where

- Y_{ij} logarithm of the pharmacokinetic endpoint for subject j at dose level i;
where number of dose groups $i = 1, 2, 3$, and $j = 1, 2, \dots, N$ where N is the number of subjects per dose group;
- α intercept parameter;
- β slope parameter;
- X_i logarithm of dose i;

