6.2 IMPORTANT PROTOCOL VIOLATIONS

Data discrepancies and deviations from the CTP will be identified for all subjects in the database (i.e., treated subjects and subjects with serious AE (SAE) which the investigator considered related to the screening procedure). Consistency check listings (for identification of violations of time windows) and a list of protocol deviations (e.g. deviations in drug administration, in blood sampling times, etc.) will be provided to be discussed at the report planning meeting (RPM). At this meeting, it will be decided whether a discrepant data value can be used in analyses or whether it must be corrected in the clinical database.

Each protocol deviation must be assessed to determine whether it is an important protocol violation (PV). For definition of important PVs, and for the process of identification of these, refer to the Boehringer Ingelheim reference document 'Protocol Violation Handling Definitions' [\(1\)](#).

If any important PVs are identified, they are to be summarised into categories and will be captured in the RPM minutes via an accompanying Excel spreadsheet [\(2\)](#). The following table contains the categories which are considered to be important PVs in this trial. If the data show other important PVs, this table will be supplemented accordingly by the time of the RPM. If substantial numbers of PVs are reported at the RPM, a decision about summarising the PVs in a tabular format will be made. Otherwise, only a PV listing will be provided.

The following [Table 6.2: 1](#) gives the important PVs for this trial.

Table 6.2: 1 Important Protocol violations

Category	Description
/ Code	
A	Entrance criteria not met
A1	Inclusion criteria violated
A2	Exclusion criteria violated
B	Informed consent
B1	Informed consent not available
B2	Informed consent too late
C	Trial medication and randomisation
C1	Incorrect trial medication administered
C2	Randomisation not followed
C3	Non-compliance
C4	Medication code broken inappropriately
C5	Incorrect administration of trial medication
D	Concomitant medication
D1	Prohibited medication use
E	Missing data
E1	Certain violations of procedures used to measure primary or secondary data
F	Incorrect timing
F1	Certain violations of time schedule used to measure primary or secondary data.

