7.3 TREATMENT COMPLIANCE

Treatment compliance will not be analysed as a specific endpoint. Any deviations from complete administration of the trial medication will be addressed in the RPM and described in the CTR.

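### Does a 90-minute cap on an infusion planned to last 90 minutes leave the plan unworkable, or CL and Vss undefined, after a mild infusion reaction?

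*Protocol*

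**What the plan says.** - **Planned duration.** Protocol 4.1.4: "In all subjects the infusion solution will be intravenously administered over 90 minutes". The synopsis gives the same duration, and the iv Flow Chart starts the infusion at 0:00 and ends it at 1:30.
- **Cap.** Under Protocol 3.3.4.1 an infusion reaction normally leads to removal. In mild transient cases needing no treatment the investigator may continue, with the limit "However, the overall infusion time must not exceed 90 minutes".
- **End-of-infusion sample.** Footnote 12 of the iv Flow Chart: "First measure after completion of infusion collection of PK sample". Protocol 6.1 gives the tolerance that applies at 1:30 as plus or minus "5 min up to including 12 h".
- **Late samples.** Protocol 5.5, 6.1 and 7.3.5 all base the PK calculations on actual sampling times. SAP 7.5.2 allows a concentration flagged for a time violation or deviation to be used in analyses based on actual times.
- **Incomplete doses.** SAP 7.3: "Any deviations from complete administration of the trial medication will be addressed in the RPM and described in the CTR". SAP 6.2 lists category C5, "Incorrect administration of trial medication". Protocol 7.3.2 names, among violations that may exclude PK data, "Incorrect dose of trial medication taken".
- **Dose in the analysis.** The power model's covariate is the "logarithm of dose i", that is, the group level. Protocol 7.3.2 and 7.3.5 and SAP 7 leave the PK parameters to the sponsor's PK procedure and its reference document.

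**The concern.** Plan and cap are the same number, so an infusion that is slowed, or paused and restarted, seems to have nowhere to go. If pauses count towards the limit, the full dose does not fit at the planned rate. If they do not, the infusion ends after 1:30 and the sample that must follow completion can fall outside its window.

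A pause can be foreseen from the protocol: section 4.1.4 tells the investigator to stop for safety concerns such as infusion reactions, and section 3.3.4.1 allows mild cases to continue.

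If the dose is cut short, CL and Vss, both secondary endpoints that scale with dose, depend on whether the nominal or the delivered amount is used. The visible text does not say which. Settling this case by case at the report planning meeting, by sponsor staff who are unblinded under Protocol 4.1.5.1, looks like an avoidable choice made after the data are seen.

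**Working it through.** **Inputs from the documents.** Infusion 0:00 to 1:30 (8:00 to 9:30), which is 90 min and reproduces the stated duration; cap 90 min; tolerance ±5 min at 1:30; next PK sample at 2:00; six active subjects in each of three iv groups.

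**Assumed.** Pauses of 5, 10, 15 and 30 min; dose spacing 1:2:4 or 1:3:9 (the doses are redacted); between-subject CV of 20% to 30%; exposure proportional to delivered dose.

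**Step 1: slack.** 90 − 90 = 0 min.

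**Step 2: timing at an unchanged rate with the full dose given.** After a pause of k minutes the infusion ends at 90 + k.
- If pauses count, any k above 0 breaks the cap.
- If they do not, the cap holds, but the sample leaves its window when 90 + k exceeds 95, that is, when k exceeds 5.
- Slowing to a fraction f of the rate from minute 30 takes 30 + 60/f minutes: 96.7 at f = 0.9 and 110 at f = 0.75, both over the cap.

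Both conditions matter. No visible passage fixes a constant rate. If the infusion simply ends at 90 minutes with less than the full dose, the cap, footnote 12 and the sample window are all met and only completeness is lost. These are logical possibilities, not suggestions for practice.

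**Step 3: individual CL and Vss.** Suppose pauses count, the rate is unchanged and the infusion stops at 90 minutes. The undelivered share is k/90. CL or Vss from the nominal dose is overstated by 1/(1 − k/90) − 1, and the geometric mean of six with one affected rises by [1/(1 − k/90)]^(1/6) − 1.

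| Pause (min) | Undelivered | Individual CL, Vss | Group geometric mean CL | End of infusion if pauses do not count |
|---|---|---|---|---|
| 5 | 5.6% | +5.9% | +1.0% | 1:35 |
| 10 | 11.1% | +12.5% | +2.0% | 1:40 |
| 15 | 16.7% | +20% | +3.1% | 1:45 |
| 30 | 33.3% | +50% | +7.0% | 2:00 |

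**Step 4: dose-proportionality slope.** With 18 subjects at 1:r:r², Sxx = 12 × (ln r)². One top-dose subject who loses 15 minutes shifts the slope by ln(r) × ln(1 − 15/90)/Sxx = −0.182/(12 × ln r).
- r = 2: −0.022. r = 3: −0.014.
- The 95% CI half-width is t(0.975, 16) × √ln(1 + CV²)/√Sxx, with t = 2.12: 0.17 to 0.26 for r = 2 and 0.11 to 0.16 for r = 3.

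The shift is at most about an eighth of the half-width (0.022/0.17 = 0.13; 0.014/0.11 = 0.13).

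**Step 5: a pause with the full dose given.** Actual times enter the calculation, so AUC, and with it CL, is not biased by the delay. Mean input time moves by no more than the length of the pause, on a profile sampled to 3528 h.

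**The case for a change.** The best case for a change is practical. During a reaction the site needs one reading of the limit, and a meeting held after the data are in cannot supply it. A definition of overall infusion time and one SAP sentence naming the dose would cost little. It is true that the term is undefined and that the visible text names no dose.

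The rest is weaker.
- The two 90-minute statements do not contradict each other. The natural reading of the second is that a reaction should not prolong the infusion.
- Footnote 12 already ties the sample to actual completion, so a delayed sample is a recorded deviation with a stated route into the analysis.
- SAP 6.2 assesses departures from the protocol. A dose cut short to obey the protocol's own cap is hardly one, so the C5 question has little substance.
- Unblinding is beside the point. CL and Vss are reported only for active subjects, and Protocol 3.2 and 4.1.5.1 make the dose level known to all. Blinding active against placebo could not protect the choice of dose in the formula.
- The procedure that governs the PK calculation is cited but not supplied, so its silence on incomplete doses cannot be assumed.
- A subject removed after a reaction goes to an end-of-trial examination and may yield no AUC to infinity, in which case the question does not arise.

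**Conclusion.** No change is needed. What remains is missing detail: one undefined term, and a dose convention left to a cited procedure. No stated rule is shown to give a wrong result. A timing conflict needs slowing or a pause, an unchanged rate and a full dose together. A bias in CL or Vss needs an incomplete dose and the use of the nominal amount, after the report planning meeting and the discretionary PK exclusion have both let the value through. Infusion start and end times are recorded and the infusion set is weighed, so analysts may have what they need to judge such a case, although the documents do not say that the weights reach the database.

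Even then, one affected subject in six moves a group's geometric mean CL by 1.0% to 3.1% for pauses up to 15 minutes and by 7.0% at 30 minutes, which is long for a reaction described as mild and transient. The slope barely moves. Protocol 7.2 calls the study exploratory and its intervals estimates only, and the primary endpoint, subjects with drug-related adverse events, is defined without reference to delivered dose. These sizes rest on assumed pauses, dose spacing and variability. How the limit is applied at the bedside is for the sponsor and investigator; nothing here favours one reading.
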